3.6.2 Exclusion criteria

Subjects presenting with any of the following criteria will not be included in the trial:

- Contraindication for usage systemic steroids
- Critically ill patients needing respiratory support
- Non-compliance with medical treatments and interventions
- Women with childbearing potential and not practicing a medically accepted contraception during the trial and a positive pregnancy test (serum or urine) before and at the end of the trial. Reliable contraception are systematic contraceptives (oral, implant, injection) and diaphragm or condoms with spermicide.
- Pregnancy and lactation.
- Participation in another trial for EAA during the last 4 weeks or not beyond the time of 4 half-lives of the medication used. In the unlikely event a subject is already in another clinical study but not for EAA, that study must be stopped and the subject may be treated according to this protocol; a latency time between the two studies does not appear

reasonable, as acute intervention is necessary for EAA. Treatment may be best done in the frame work of this protocol.

3.6.3 *Withdrawal criteria*

Subjects can withdraw their consent at their own request without given reasons at all time during the trial. This should be without disadvantages for the subject. However the investigator should try to perform a final visit to get concluding findings of investigation.

Subjects may be withdrawn from the trial for the following reasons

- At their own request or at request of the legal representative
- If, in the investigator's opinion, continuation of the trial would be detrimental to the subject's well-being
- If there occur major side effects of the study medication, which make it irresponsible to continue with the study medication.
- If the patient's condition deteriorates in a way, that an intensification of the therapy is necessary and additional open steroid treatment is not sufficient to alleviate the condition.
- For women, if it becomes known that the subject is pregnant.

The investigator decides about withdrawal of subjects from the clinical trial in case of occurrence of criteria mentioned above.

In all cases, the reason for withdrawal must be recorded in the CRF and in the subject's medical records. In case of withdrawal of a subject at his/her own request, as far as possible the reason should be asked for and documented. The subject must be followed up and as far as possible, all examinations scheduled for the final trial day should be performed and documented.

All on-going serious adverse events of withdrawn subjects have to be followed up see 6.2.1.3.

Withdrawn subjects will not be replaced.

3.6.4 *Premature closure of the clinical trial*

The following reasons the whole trial may be discontinued at the discretion of the sponsor:

- New risks for subjects become known.
- Inefficacy of the trial medication becomes evident.
- Occurrence of AEs unknown to date in respect of their nature, severity, and duration or the unexpected increase in the incidence of known AEs.
- Medical or ethical reasons affecting disadvantageous the continued performance of the trial.

The ethic committees (EC) and the competent authority must then be informed. Should the trial be closed prematurely, all trial material must be returned to or fetched by the monitor.

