- **Cyclosporine:** Increased activity of both cyclosporine and corticosteroids may occur when the two are used concurrently. Convulsions have been reported with concurrent use.

- **Digitalis:** Patients on digitalis glycosides may be at increased risk of arrhythmias due to hypokalemia.
- **Estrogens, including oral contraceptives:** Estrogens may decrease the hepatic metabolism of certain corticosteroids thereby increasing their effect.
- **NSAIDs including aspirin and salicylates:** Concomitant use of aspirin or other non-steroidal anti-inflammatory agents and corticosteroids increases the risk of gastrointestinal side effects. Aspirin should be used cautiously in conjunction with corticosteroids in hypoprothrombinemia. The clearance of salicylates may be increased with concurrent use of corticosteroids.
- **Potassium depleting agents (e.g., diuretics, Amphotericin B):** When corticosteroids are administered concomitantly with potassium-depleting agents, patients should be observed closely for development of hypokalemia.
- **Skin tests:** Corticosteroids may suppress reactions to skin tests.
- **Toxoids and live or inactivated vaccines:** Due to inhibition of antibody response, patients on prolonged corticosteroid therapy may exhibit a diminished response to toxoids and live or inactivated vaccines. Corticosteroids may also potentiate the replication of some organisms contained in live attenuated vaccines

Warnings and precautions

Alterations in Endocrine Function

Hypothalamic-pituitary-adrenal (HPA) axis suppression, Cushing's syndrome, and hyperglycemia. Monitor patients for these conditions with chronic use.

Corticosteroids can produce reversible HPA axis suppression with the potential for glucocorticosteroid insufficiency after withdrawal of treatment. Drug induced secondary adrenocortical insufficiency may be minimized by gradual reduction of dosage. This type of relative insufficiency may persist for months after discontinuation of therapy; therefore, in any situation of stress occurring during that period, hormone therapy should be reinstated.

Since mineralocorticoid secretion may be impaired, salt and/or a mineralocorticoid should be administered concurrently. Mineralocorticoid supplementation is of particular importance in infancy.

Metabolic clearance of corticosteroids is decreased in hypothyroid patients and increased in hyperthyroid patients. Changes in thyroid status of the patient may necessitate adjustment in dosage.

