4.4 Open rescue treatment if lung function does not improve

With removal of the allergen by hospitalization and cleaning of the home from offending allergens which is usually done during the initial hospital stay, and after application of the 3d steroid boost to all subjects, a steady improvement in lung function is anticipated. This will be closely monitored by monthly lung function measurements in the first 3 months and at 6 months or additional visits at the discretion of the treating physician. FVC (% predicted) is expected to increase from visit to visit.

If this is not the case, continuing allergen exposure must be considered and a re-evaluation of the allergen elimination has to be performed.

If there is no appropriate improvement of lung function despite appropriate allergen elimination, an open rescue treatment with oral prednisolone (0.5 mg/kg bw/d) should be given till the patient's lung function improves. An alternative may be pulsed methylprednisolone (10 mg/kg bw/d). Extra visits at the discretion of the treating physician may be scheduled.

If the result of the oral prednisolone is not satisfying, re-evaluation of the diagnosis and possibly de-blinding of the study medication should be considered. Alternative medication, including steroid sparing drugs may be considered.

All rescue treatments necessary will be recorded and the cumulative amount of steroids necessary used as a secondary outcome variable.

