7.3 Efficacy analyses

Efficacy:

The analyses will be specified more detailed in the statistical analysis plan (SAP). Descriptive statistics of qualitative data will consist of absolute and relative frequencies. For quantitative data the number of observations, mean, standard deviation, minimum and maximum will be presented.

The primary population for the analyses of efficacy is the randomized Population without major protocol violations.

7.3.1 *Definition and analysis of primary endpoint*

The primary analysis variable is the improvement in FVC (difference after 6 months and baseline). The 6 months and baseline FVC values will be given in percent deviation from the norm values tabulated by Quanjer PH., et al. 2013.

A difference between the changes in placebo and active treatment is considered not significant if FVC differences are < 7%. The working hypothesis of the study is that the placebo is not inferior to the prednisolone intervention.

The improvement in FVC will be compared between groups within an analysis of covariance (ANCOVA). Treatment will serve as a fixed factor and the baseline FVC value as a covariate. The primary analysis population will consist of all randomized patients without any major protocol violations. The two-sided 90% confidence interval for the treatment difference will be calculated. Sensitivity analyses will be performed by analyzing the same analysis model for all randomized patients. Additionally, the primary parameter will be analyzed by ANCOVA with additional terms for sex and height. Center effects will be explored by descriptive statistics. Missing values will not be replaced.

If appropriate, a Bayesian analysis with a suited prior distribution will be considered. This will be specified in the statistical analysis plan (SAP).

7.3.2 *Analysis of secondary endpoints*

All analysis of secondary endpoint will be interpreted purely exploratory. Descriptive statistics will be displayed for all

- Response according to the primary analysis variable: Each patient will be classified as a responder or non-responder. A patient is considered as a responder, if the FVC value after 6 months is more than or equal to 93% of the norm values tabulated by Quanjer PH., et al. 2013 and if the patient did not take any glucocorticoid rescue medication. Responders will be analysed by a Chi-Square Test.

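### Section 3.6.3 has no status of off study medication but still in follow-up, and leaves the month-6 FVC and new adverse events after withdrawal unsettled

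*Protocol*

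**What the plan says.** Section 3.6.3 opens its list permissively: "Subjects may be withdrawn from the trial for the following reasons". Two entries matter here. One is about tolerability of the capsules: "If there occur major side effects of the study medication, which make it irresponsible to continue with the study medication". The other is deterioration such that "an intensification of the therapy is necessary and additional open steroid treatment is not sufficient to alleviate the condition". The decision is individual: "The investigator decides about withdrawal of subjects from the clinical trial in case of occurrence of criteria mentioned above".

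For withdrawn patients, the same section requires follow-up and adds, qualified by feasibility, that "all examinations scheduled for the final trial day should be performed and documented". It gives no date for those examinations. It also requires follow-up of ongoing serious adverse events, and withdrawn patients are not replaced.

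Other sections bear on the same patients:
- Section 3.5.2 allows unblinding only in an emergency and makes withdrawal compulsory afterwards.
- Section 4.4 says that, when oral prednisolone rescue is unsatisfactory, de-blinding should be considered. It continues: "Alternative medication, including steroid sparing drugs may be considered".
- Section 6.2.1.3 runs adverse event observation from first intake to the 6-month final visit. Section 6.2.1.4 follows existing events to their outcome, for at most 90 days after the end of the trial.
- Section 7.3.1 defines the primary variable as the 6-month minus baseline difference in FVC, analysed by ANCOVA, and states: "Missing values will not be replaced".

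**The concern.** Intolerance of the capsules is a reason to stop the capsules. The only consequence the protocol attaches to it is possible exit from the trial. The same holds for deterioration beyond open rescue. These are the patients whose outcomes the trial most needs. Placebo is the experimental arm and the claim is non-inferiority, so deterioration on placebo is the evidence that could refute it.

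If such a patient has no FVC near day 168, the ANCOVA drops the patient. Rerunning the model on all randomized patients cannot restore a value that was never measured, and no later analysis plan can either. The responder endpoint needs the same month-6 FVC. Rescue steroid use is expressed per 6 months, so early exit truncates it. New adverse events after exit may go unrecorded. Because exit is decided case by case across about 40 sites, missingness can depend on outcome and on local habit.

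**Working it through.** **1. What is fixed for each route out of the trial**

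| Route | Is withdrawal required? | FVC at day 168 | New adverse events to month 6 |
|---|---|---|---|
| Capsules stopped for side effects (3.6.3) | No, investigator decides | Final-day examinations where feasible; timing not given | Not stated |
| Open rescue insufficient (3.6.3, 4.4) | No, investigator decides | As above | Not stated |
| De-blinded after failed rescue (4.4, then 3.5.2) | Yes | As above | Not stated |
| Consent withdrawn (3.6.3) | Patient's choice | A final visit is to be attempted; timing not given | Not stated |

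Table 1 places the final visit at day 168 (148 to 188) and includes FVC. An FVC taken at exit in month 2 would satisfy one reading of section 3.6.3, but it is not the primary variable of section 7.3.1.

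**2. The plan's own figures**

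Planned loss (section 3.2): 45 − 40 = 5, and 5/45 = 11.1%. Section 7.1 describes the 40 as evaluable per protocol, so the 5 cover any major violation. They do not forecast withdrawals for harm or deterioration.

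The power of 58% (section 7.1: one-sided alpha 0.05, 40 patients, bound 7%, baseline correlation 0.4) cannot be reproduced, because no standard deviation is given. Solving backwards for a two-sample t-test with 20 per arm and no true difference gives an effective standard deviation of 11.8 points. At that value, power falls to 54% with 36 evaluable patients and 50% with 32. Losses therefore cost precision as well as risking bias.

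**3. Illustrative bias**

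Assume that k of n placebo patients have no month-6 FVC and would have scored d points below the rest. The mean of those observed then exceeds the full-arm mean by k × d / n. The values of k and d, and placing all losses in the placebo arm, are assumptions. Taking n = 40/2 = 20 and the bound as 7 points:

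| k | d | Shift | Share of bound |
|---|---|---|---|
| 2 | 10 | 2 × 10/20 = 1.0 | 1.0/7 = 14% |
| 3 | 10 | 3 × 10/20 = 1.5 | 1.5/7 = 21% |
| 2 | 20 | 2 × 20/20 = 2.0 | 2.0/7 = 29% |
| 3 | 20 | 3 × 20/20 = 3.0 | 3.0/7 = 43% |

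A wider assumed range, 5% to 25% of the arm missing with the same deficits, gives 0.05 × 10 = 0.5 to 0.25 × 20 = 5.0 points, or 7% to 71% of the bound. With all 45 randomized, arms would hold 22 or 23, and the extremes of the table become 2 × 10/23 = 0.9 and 3 × 20/22 = 2.7.

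The bias in the comparison is the difference between the arms' shifts. Equal losses with equal deficits in both arms would cancel.

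**The case against.** The defence has real weight. Withdrawal is optional, no sentence says that stopping capsules ends participation, and section 3.6.3 requires withdrawn patients to be followed. Section 6.2.1.4 follows existing adverse events to outcome, so the event that prompted a withdrawal for side effects is itself followed. Section 6.2.1.3 does not shorten the observation period for withdrawn patients. The primary population, as named in sections 7.3 and 7.3.1, excludes major protocol violations, so it may omit these patients whatever is collected. A month-6 FVC taken on intensified therapy may also show a smaller deficit than assumed above.

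Three stronger readings are therefore unsupported:
- A reader might infer that these patients necessarily lose their month-6 FVC and the rest of safety observation. The text leaves both open.
- A reader might infer that sections 3.6.3 and 4.4 contradict each other on failed rescue. Both are permissive and can hold together. The conflict is between section 3.5.2 (emergency unblinding only, then compulsory withdrawal) and section 4.4 (consider de-blinding).
- A reader might connect early exit with the warning in section 4.2.3 that "This type of relative insufficiency may persist for months after discontinuation of therapy". That is general corticosteroid text, and the same section says such endocrine effects are not expected at the trial's doses.

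What survives is that the follow-up duty lacks a date, is softened by feasibility, and does not mention new adverse events.

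**Conclusion.** The point holds as a gap in the plan. Section 3.6.3 does not separate stopping study medication from leaving the trial. It also does not secure the day-168 FVC or collection of new adverse events for patients who stop for harm or deterioration. On the de-blinding route, withdrawal is not even discretionary.

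Outcome-related loss of month-6 data can therefore follow from the protocol as written. In the all-randomized or ITT comparison it could favour placebo if losses are concentrated among placebo failures. Section 7.2 calls both the ITT and the per-protocol set primary, so the status of that comparison is itself unclear. The responder, rescue-steroid and safety comparisons are exposed too.

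The size is unknown. The 1.0 to 3.0 points (14% to 43% of the bound) show what assumed losses would do and do not estimate the bias.

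**What to change.** In section 3.6.3, define stopping of study medication separately from withdrawal from follow-up. State that patients who stop capsules, need treatment beyond open steroids or are unblinded keep the scheduled visits, the day-168 FVC and adverse event collection to month 6, unless they or their representatives refuse follow-up. Record the date and reason for stopping capsules. Reconcile sections 3.5.2, 3.6.3 and 4.4 on unblinding and its consequence. In the same amendment, correct section 6.2.1.3, which calls the 6-month visit visit 3 where Table 1 has visit 4, and the pointer in section 3.6.3 to 6.2.1.3, since the follow-up rule is in 6.2.1.4. Clinical decisions on stopping and rescue stay as they are.

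The cost is amendment wording and one CRF entry. Section 5 treats most visits and spirometry as routine care, but the questionnaires and the adverse event documentation at the day-126 telephone contact are trial-specific and would continue for these patients. The downside is that some month-6 values will come from patients off study drug or on other therapy, and the per-protocol set may still exclude them. The gain is mainly in the all-randomized, responder, rescue-steroid and safety analyses.

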4. TRIAL TREATMENTS

4.1 Identification and elimination of EAA Allergens

A) Identification of possible allergens with the following questions (shortly after diagnosis has been made):

	Yes	No	Comment
Birds or other pets at home or in the garden?			
Bird cage/chicken house/pigeon loft at home or in garden?			
Down feathers in bed/clothing?			
Fungi at home?			
Humid stonework, wallpaper, furnishing or carpet?			
Water container/tabletop fountain/swimming pool/whirlpool at home?			
Contact to hay/straw/feed grain?			
Air condition at home?			
Potted plants at home?			
Contact to organic waste or compost?			

A ground plan of house and garden has to be drawn together with the patient or his parents with marking the information asked above; please send this plan to the study center.

B) High quality and standardized serological allergen/precipitin identification in experienced labs, e.g. [name], Internal Medicine, Klinikum Großhadern, LMU or [name], Bonn.
Elimination of antigen (shortly after diagnosis has been made):

- If birds or other pets at home
 - give them away, also the birdcage
 - cleaning of all tissues (i.e. carpet, curtains etc.)
- elimination of down feathers in bed/clothing
- no water container/nebulizer
- no swimming pool, whirlpool, tabletop fountain
- avoid contact to hay, straw, feed grain
- fungi:
 - humidity in room air < 65%
 - daily forced ventilation of the rooms (open window wide and short time)
 - elimination of contaminated wallpaper, furnishing and carpet
 - humid stonework -> repair if possible

C) Control by a site visit to determine independently that elimination of antigen was successful (Trial day 56 (49 - 63), at home)

If elimination was not successful: repeat consultation and education (issue 1. and 2.).

	Yes	No	Comment
Has the antigen identified above been eliminated successfully?			

4.2 Investigational treatments

4.2.1 General information about investigational medicinal product (IMP)

International nonproprietary name (INN): prednisolone
Formulation: hard capsules (capsules with tablets)
Manufacturer: Pharmacy University Medical Center Mainz

Comparative Product (Placebo)

Generic name: Placebo (capsules with placebo tablets)
Formulation: hard capsules
Manufacturer: Pharmacy department University Medical Center Mainz

4.2.2 Therapeutic effects

Prednisolone is a synthetic corticosteroid, which is mainly used as a non-specific anti-inflammatory and immunosuppressive drug. It modifies the body's immune response to diverse stimuli. As Prednisolone is an analogue of the hormone hydrocortisone it may cause dose – and time-dependent various metabolic effects. Prednisolone is indicated in the treatment of various conditions such as for example rheumatic diseases, chronic inflammatory bowel disease, allergic or hematological diseases. In pneumology it is used in asthma therapy as well as in many other pulmonary diseases, including interstitial lung diseases.

4.2.3 Known side effects

Side effects

Common adverse reactions for corticosteroids include fluid retention, alteration in glucose tolerance, elevation in blood pressure, behavioural and mood changes, increased appetite and weight gain.

Allergic Reactions: Anaphylactoid reaction, anaphylaxis, angioedema

Cardiovascular: Bradycardia, cardiac arrest, cardiac arrhythmias, cardiac enlargement, circulatory collapse, congestive heart failure, fat embolism, hypertension, hypertrophic cardiomyopathy in premature infants, myocardial rupture following recent myocardial infarction, pulmonary edema, syncope, tachycardia, thromboembolism, thrombophlebitis, vasculitis

Dermatologic: Acne, allergic dermatitis, cutaneous and subcutaneous atrophy, dry scalp, edema, facial erythema, hyper or hypo-pigmentation, impaired wound healing, increased sweating, petechiae and ecchymoses, rash, sterile abscess, striae, suppressed reactions to skin tests, thin fragile skin, thinning scalp hair, urticaria

Endocrine: Abnormal fat deposits, decreased carbohydrate tolerance, development of Cushingoid state, hirsutism, manifestations of latent diabetes mellitus and increased requirements for insulin or oral hypoglycemic agents in diabetics, menstrual irregularities, moon facies, secondary adrenocortical and pituitary unresponsiveness (particularly in times of stress, as in trauma, surgery or illness), suppression of growth in children

Fluid and Electrolyte Disturbances: Fluid retention, potassium loss, hypertension, hypokalemic alkalosis, sodium retention

Gastrointestinal: Abdominal distention, elevation in serum liver enzymes levels (usually reversible upon discontinuation), hepatomegaly, hiccups, malaise, nausea, pancreatitis, peptic ulcer with possible perforation and hemorrhage, ulcerative esophagitis

General: Increased appetite and weight gain

Metabolic: Negative nitrogen balance due to protein catabolism

Musculoskeletal: Aseptic necrosis of femoral and humeral heads, charcot-like arthropathy, loss of muscle mass, muscle weakness, osteoporosis, pathologic fracture of long bones, steroid myopathy, tendon rupture, vertebral compression fractures

Neurological: Arachnoiditis, convulsions, depression, emotional instability, euphoria, headache, increased intracranial pressure with papilledema (pseudo-tumor cerebri) usually following discontinuation of treatment, insomnia, meningitis, mood swings, neuritis, neuropathy, paraparesis/paraplegia, paresthesia, personality changes, sensory disturbances, vertigo

Ophthalmic: Exophthalmos, glaucoma, increased intraocular pressure, and posterior subcapsular cataracts

Reproductive: Alteration in motility and number of spermatozoa

Drug interactions

- **Aminoglutethimide:** Aminoglutethimide may lead to loss of corticosteroid-induced adrenal suppression.
- **Amphotericin B:** There have been cases reported in which concomitant use of Amphotericin B and hydrocortisone was followed by cardiac enlargement and congestive heart failure (see also **Potassium depleting agents**).
- **Anticholinesterase agents:** Concomitant use of anticholinesterase agents and corticosteroids may produce severe weakness in patients with myasthenia gravis. If possible, anticholinesterase agents should be withdrawn at least 24 hours before initiating corticosteroid therapy.
- **Anticoagulant agents:** Coadministration of corticosteroids and warfarin usually results in inhibition of response to warfarin, although there have been some conflicting reports. Therefore, coagulation indices should be monitored frequently to maintain the desired anticoagulant effect.
- **Antidiabetic agents:** **Antidiabetic agents:** Because corticosteroids may increase blood glucose concentrations, dosage adjustments of antidiabetic agents may be required.
Antitubercular drugs: Serum concentrations of isoniazid may be decreased.
- **CYP 3A4 inducers (e.g., barbiturates, phenytoin, carbamazepine, and rifampin):** Drugs such as barbiturates, phenytoin, ephedrine, and rifampin, which induce hepatic microsomal drug metabolizing enzyme activity may enhance metabolism of prednisolone and require that the dosage prednisolone be increased.
- **CYP 3A4 inhibitors (e.g., ketoconazole, macrolide antibiotics):** Ketoconazole has been reported to decrease the metabolism of certain corticosteroids by up to 60% leading to an increased risk of corticosteroid side effects.
- **Cholestyramine:** Cholestyramine may increase the clearance of corticosteroids.
- **Cyclosporine:** Increased activity of both cyclosporine and corticosteroids may occur when the two are used concurrently. Convulsions have been reported with concurrent use.

- **Digitalis:** Patients on digitalis glycosides may be at increased risk of arrhythmias due to hypokalemia.
- **Estrogens, including oral contraceptives:** Estrogens may decrease the hepatic metabolism of certain corticosteroids thereby increasing their effect.
- **NSAIDs including aspirin and salicylates:** Concomitant use of aspirin or other non-steroidal anti-inflammatory agents and corticosteroids increases the risk of gastrointestinal side effects. Aspirin should be used cautiously in conjunction with corticosteroids in hypoprothrombinemia. The clearance of salicylates may be increased with concurrent use of corticosteroids.
- **Potassium depleting agents (e.g., diuretics, Amphotericin B):** When corticosteroids are administered concomitantly with potassium-depleting agents, patients should be observed closely for development of hypokalemia.
- **Skin tests:** Corticosteroids may suppress reactions to skin tests.
- **Toxoids and live or inactivated vaccines:** Due to inhibition of antibody response, patients on prolonged corticosteroid therapy may exhibit a diminished response to toxoids and live or inactivated vaccines. Corticosteroids may also potentiate the replication of some organisms contained in live attenuated vaccines

Warnings and precautions

Alterations in Endocrine Function

Hypothalamic-pituitary-adrenal (HPA) axis suppression, Cushing's syndrome, and hyperglycemia. Monitor patients for these conditions with chronic use.

Corticosteroids can produce reversible HPA axis suppression with the potential for glucocorticosteroid insufficiency after withdrawal of treatment. Drug induced secondary adrenocortical insufficiency may be minimized by gradual reduction of dosage. This type of relative insufficiency may persist for months after discontinuation of therapy; therefore, in any situation of stress occurring during that period, hormone therapy should be reinstated.

Since mineralocorticoid secretion may be impaired, salt and/or a mineralocorticoid should be administered concurrently. Mineralocorticoid supplementation is of particular importance in infancy.

Metabolic clearance of corticosteroids is decreased in hypothyroid patients and increased in hyperthyroid patients. Changes in thyroid status of the patient may necessitate adjustment in dosage.

With the doses suggested in this trial such alterations in endocrine function are not expected to occur.

Increased Risks Related to Infections

Corticosteroids may increase the risks related to infections with any pathogen, including viral, bacterial, fungal, protozoan, or helminthic infections. The degree to which the dose, route and duration of corticosteroid administration correlates with the specific risks of infection is not well characterized, however, with increasing doses of corticosteroids, the rate of occurrence of infectious complications increases.

Corticosteroids may mask some signs of infection and may reduce resistance to new infections.

Corticosteroids may exacerbate infections and increase risk of disseminated infection.

The use of prednisolone in active tuberculosis should be restricted to those cases of fulminating or disseminated tuberculosis in which the corticosteroid is used for the management of the disease in conjunction with an appropriate antituberculous regimen.

Chickenpox and measles can have a more serious or even fatal course in non-immune children or adults on corticosteroids. In children or adults who have not had these diseases, particular care should be taken to avoid exposure. If a patient is exposed to chickenpox, prophylaxis with varicella zoster immune globulin (VZIG) may be indicated. If patient is exposed to measles, prophylaxis with pooled intramuscular immunoglobulin (IG) may be indicated. If chickenpox develops, treatment with antiviral agents may be considered.

Corticosteroids should be used with great care in patients with known or suspected *Strongyloides* (threadworm) infestation. In such patients, corticosteroid-induced immunosuppression may lead to *Strongyloides* hyperinfection and dissemination with widespread larval migration, often accompanied by severe enterocolitis and potentially fatal gram-negative septicemia.

Corticosteroids may exacerbate systemic fungal infections and therefore should not be used in the presence of such infections unless they are needed to control drug reactions.

Corticosteroids may increase risk of reactivation or exacerbation of latent infection.

If corticosteroids are indicated in patients with latent tuberculosis or tuberculin reactivity, close observation is necessary as reactivation of the disease may occur. During prolonged corticosteroid therapy, these patients should receive chemoprophylaxis.

Corticosteroids may activate latent amebiasis. Therefore, it is recommended that latent or active amebiasis be ruled out before initiating corticosteroid therapy in any patient who has spent time in the tropics or in any patient with unexplained diarrhoea.

Corticosteroids should not be used in cerebral malaria.

Alterations in Cardiovascular/Renal Function

Corticosteroids can cause elevation of blood pressure, salt and water retention, and increased excretion of potassium and calcium. These effects are less likely to occur with the synthetic derivatives except when used in large doses. Dietary salt restriction and potassium supplementation may be necessary. These agents should be used with caution in patients with hypertension, congestive heart failure, or renal insufficiency.

Literature reports suggest an association between use of corticosteroids and left ventricular free wall rupture after a recent myocardial infarction; therefore, therapy with corticosteroids should be used with caution in these patients.

Use in Patients with Gastrointestinal Disorders

There is an increased risk of gastrointestinal perforation in patients with certain GI disorders. Signs of GI perforation, such as peritoneal irritation, may be masked in patients receiving corticosteroids.

Corticosteroids should be used with caution if there is a probability of impending perforation, abscess or other pyogenic infections; diverticulitis; fresh intestinal anastomoses; and active or latent peptic ulcer.

Behavioral and Mood Disturbances

Corticosteroid use may be associated with central nervous system effects ranging from euphoria, insomnia, mood swings, personality changes, and severe depression, to frank psychotic manifestations. Also, existing emotional instability or psychotic tendencies may be aggravated by corticosteroids.

Decrease in Bone Density

Corticosteroids decrease bone formation and increase bone resorption both through their effect on calcium regulation (i.e., decreasing absorption and increasing excretion) and inhibition of osteoblast function. This, together with a decrease in the protein matrix of the bone secondary to an increase in protein catabolism, and reduced sex hormone production, may lead to inhibition of bone growth in children and adolescents and the development of osteoporosis at any age. Special consideration should be given to patients at increased risk of osteoporosis (i.e., postmenopausal women) before initiating corticosteroid therapy and bone density should be monitored in patients on long-term corticosteroid therapy.

Ophthalmic Effects

Prolonged use of corticosteroids may produce posterior subcapsular cataracts, glaucoma with possible damage to the optic nerves, and may enhance the establishment of secondary ocular infections due to fungi or viruses. The use of oral corticosteroids is not recommended in the treatment of optic neuritis and may lead to an increase in the risk of new episodes. Intraocular pressure may become elevated in some individuals. If steroid therapy is continued for more than 6 weeks, intraocular pressure should be monitored.

Patients with Ocular Herpes Simplex

Corticosteroids should be used cautiously in patients with ocular herpes simplex because of possible corneal perforation. Corticosteroids should not be used in active ocular herpes simplex.

Vaccination

Administration of live or live attenuated vaccines is contraindicated in patients receiving immunosuppressive doses of corticosteroids. Killed or inactivated vaccines may be administered, however, the response to such vaccines cannot be predicted. Immunization procedures may be undertaken in patients who are receiving corticosteroids as replacement therapy, e.g., for Addison's disease.

While on corticosteroid therapy, patients should not be vaccinated against smallpox. Other immunization procedures should not be undertaken in patients who are on corticosteroids, especially on high dose, because of possible hazards of neurological complications and a lack of antibody response.

Effect on Growth and Development

Long-term use of corticosteroids can have negative effects on growth and development in children. Growth and development of pediatric patients on prolonged corticosteroid therapy should be carefully monitored.

Use in Pregnancy

Prednisolone can cause fetal harm when administered to a pregnant woman. Human and animal studies suggest that use of corticosteroids during the first trimester of pregnancy is associated with an increased risk of orofacial clefts, intrauterine growth restriction and decreased birth weight. If this drug is used during pregnancy, or if the patient becomes pregnant while using this drug, the patient should be apprised of the potential hazard to the foetus.

Neuromuscular Effects

An acute myopathy has been observed with the use of high doses of corticosteroids, most often occurring in patients with disorders of neuromuscular transmission (e.g., myasthenia gravis), or in patients receiving concomitant therapy with neuromuscular blocking drugs (e.g., pancuronium). This acute myopathy is generalized, may involve ocular and respiratory muscles, and may result in quadriplegia. Elevation of creatine kinase may occur. Clinical improvement or recovery after stopping corticosteroids may require weeks to years.

Kaposi's Sarcoma

Kaposi's sarcoma has been reported to occur in patients receiving corticosteroid therapy, most often for chronic conditions. Discontinuation of corticosteroids may result in clinical improvement.

